5.1 Study Design

The China Micra™ Transcatheter Pacing Study is a prospective, multi-center, single arm human clinical trial utilizing OPC to confirm the safety and efficacy profile of the Micra TPS for regulatory approval in China. All study sites will be in China. Subjects successfully implanted with the Micra TPS in all sites will be followed at implant/pre-discharge, 1-month, 3-months, and 6-months, and at 6-month intervals thereafter (if applicable) through study closure. The overall follow-up period of China Micra™ Transcatheter Pacing Study will end when the last enrolled subject has 6 months follow-up.

Figure 1: Study Flow Chart

The China Micra™ Transcatheter Pacing study will be conducted at 7 sites in China. The study will enroll a total of 82 subjects. All subjects with chronically implanted Micra devices are expected to complete 6 months post implant follow-up visits for the study objective analyses.

It is estimated that study enrollment will be completed in 6 months. The estimated participation duration of each subject will be from 6 months to 12 months if the enrollment can be completed within 6 months. The estimated duration of whole clinical trial will be approximately 1 year including 6 months enrollment and 6 months follow-up.

5.2 Study Population

The China Micra™ Transcatheter Pacing study will be conducted in China. As such, the study population to be enrolled in the study will strictly be Chinese.

Ethics Committee approval of the China Micra™ Transcatheter Pacing Study CIP and Informed Consent Form must be obtained prior to enrolling patients in the study.

Subjects are considered enrolled in the study upon signing the informed consent and meeting all the inclusion and none of the exclusion criteria. Informed consent must be obtained prior to performing any study-related procedures. Subjects will be assessed to ensure that they meet all the inclusion and none of the exclusion criteria.

5.3 Inclusion Criteria

Table 2: Inclusion Criteria

INCLUSION Criteria	
Criteria	Rationale
Subjects who have a Class I or II indication for implantation of a single chamber ventricular pacemaker according to ACC/AHA/HRS 2008 guidelines ⁴ and China guideline. ⁵	Study will be evaluated in the standard patient population that is indicated for the device under evaluation.
Subjects who are willing to participate in study through consent and willing to undergo study specific required procedures with expectancy of geographically stable for follow up duration.	Ensure ascertainment of data required for clinical evaluation.
Subjects who are at least 18 years of age.	Ensure age is appropriate to provide informed consent.

5.4 Exclusion Criteria

Table 3: Exclusion Criteria

EXCLUSION Criteria	
Criteria	Rationale
Subject has an existing or prior pacemaker, ICD or CRT device implant.	Avoid possible confounding factors (i.e. complications due to device change-outs).
Subject has unstable angina pectoris or has had an acute myocardial infarction (AMI) in the 30 days prior to eligibility assessment.	Avoid possible confounding factors (i.e. environment more susceptible to complications due to pre-existing conditions).
Subjects with current implantation of neurostimulator or any other chronically implanted device which uses current in the body. Note that a temporary pacing wire is allowed.	Necessary to avoid any possible electrical interference with Micra device.
Subjects with a mechanical tricuspid valve, implanted vena cava filter, or left ventricular assist device (LVAD).	Necessary to avoid electrical or mechanical interference when placing Micra device.
Subjects who are morbidly obese and physician believes telemetry communication of ≤ 5 inches (12.5 cm) could not be obtained with programmer head.	Necessary to ensure ability to communicate with programmer.
Subjects whose femoral venous anatomy is unable to accommodate a 23 French introducer sheath or implant on the right side of the heart (for example, due to obstructions or severe tortuosity) in the opinion of the implanter.	Necessary to place Micra introducer sheath.
Subjects who are considered as unable to tolerate an urgent sternotomy	Necessary in case of emergency where urgent vascular surgery would be required
Subjects with a known intolerance to Nickel-Titanium (Nitinol) Alloy.	Necessary since Micra tines are comprised of Nitinol material.
Subjects for whom a single dose of 1.0mg dexamethasone acetate may be contraindicated.	Necessary due to steroid material on Micra electrode (standard exclusion for all pacing studies with steroid on the electrode).

Subjects with a life expectancy of less than 12-months.	Standard exclusion criteria to ensure study cohort is expected to survive to the time of endpoint evaluation.
Subjects who are currently enrolled or planning to participate in a potentially confounding drug or device trial during this study. Co-enrollment in concurrent trials is only allowed when document pre-approval is obtained from the Medtronic study manager.	Standard exclusion criteria to avoid confounding procedural requirements due to multiple experimental studies.
Pregnant women or breastfeeding women, or women of child bearing potential and who are not on a reliable form of birth regulation method or abstinence.	Pregnant women are excluded to avoid harm to the fetus caused by fluoroscopy requirements.
Subjects with exclusion criteria required by local law (age or other).	Standard exclusion criteria to comply with any additional local requirements which may apply.
Subjects with medical condition which precludes patient from participation in the opinion of the Investigator	Standard exclusion criteria to apply medical discretion in subject selection.

5.5 Minimization of Bias

Selection of subjects, treatment of subjects, and evaluation of study data are potential sources of bias. Below are methods incorporated in the study design to minimize potential bias include (but are not limited to):

- Subjects will be screened to confirm eligibility for enrollment with protocol pre-defined inclusion/exclusion criteria
- Demographics and medical history will be collected at baseline to assess possible characteristics that may influence endpoints
- Data collection requirements and study procedures will be standardized across all study sites
- All study sites will follow the same version(s) of the CIP and Case Report Forms (CRFs)
- The maximum enrollment number from a single site should not exceed 50% of the total study size
- All study site and Medtronic personnel will be trained using standardized training materials
- Regular monitoring visits will be conducted to verify adherence to the CIP and source data

- An independent CEC will be utilized to regularly review and adjudicate reported AEs
- All implanters in the study will be experienced in the implant of pacemaker systems and receive standardized training for the implant of the Micra TPS
- Final analysis of the study objectives will be carried out as pre-specified in this protocol

5.6 Study Procedures

All subjects enrolled in this study will be prospectively followed from implant, pre-hospital discharge, 1 month, 3 months and 6 months, and at 6-month intervals thereafter through study closure. Subjects must be seen in-office for all follow-up visits. The study visits window is shown in **Table 4**.

Table 4: Study Visits Window

Visit	Visit Window
Implant	within 30 days after baseline
Pre-hospital discharge	within 7 days after implant
1-month	23 to 45 days after implant
3-month	77 to 105 days after implant
6-month	183 to 204 days after implant
12-month*	351 to 380 days after implant

**optional visit*

Clinical data will be collected at baseline, implant/pre-hospital discharge (PHD), 1-month, 3-month, 6-month post-implant visits and at 6-month intervals thereafter, if applicable, through study closure. Data will be collected using electronic case report forms (eCRFs) using an electronic data management system for clinical studies. Data will be stored in a secure, password-protected database, which will be backed up nightly. Data will be reviewed using programmed and manual data checks. Data queries will be made available to study sites for resolution. Study management reports will be generated by Medtronic to monitor data quality and study progress. At the end of the study, the data will be frozen and retained indefinitely by Medtronic. Data collection requirements are summarized in **Table 5**.

Table 5: Summary of Data Collection and Frequency

	Enrollment /Baseline	Procedure /PHD	Follow-up*	Exit
Confirm Eligibility	X			
Consent	X			
Physical Exam, Demographics	X			
Medical History	X			
Procedure Details		X		
Anticoagulation Methods		X		
Device/System Information		X	X	X
Electrical Measurements & Device Interrogations		X	X	
Device Disposition				X
Adverse Events assessment		X	X	X
Adverse Events	Upon Occurrence			
System Modification	Upon Occurrence			
Device Deficiency	Upon Occurrence			
Deaths	Upon Occurrence			
Protocol Deviations	Upon Occurrence			

* Follow up includes 1-month, 3-month, 6-month post-implant visits and at 6-month intervals thereafter through study closure if applicable.

6. Determination of Sample Size

6.1 Total Enrollment Size

The study will require an enrollment size of 82. The study size is calculated based on statistical hypothesis, assumed expected performance, and projected attrition.

The study pass/fail criteria are based on statistical hypothesis and final analysis results. The analysis of study primary objective will be 6-month success rate comparing to the pre-specified OPC. If the 95% 2-sided confidence interval (CI) lower bound for the probability of freedom from Micra TPS and/or procedure related major complication is greater than 83%, the study will be considered yielding a positive result, demonstrating the success rate is higher than expected values, i.e. study objective will be met.

The study attrition will include all scenarios that result in enrolled subject not being included in the analysis. The common reasons are due to serious protocol deviations (if it affects performance evaluation). Other scenarios may include: Micra implant was not carried out or not successful, follow-up visit not completed per study requirement, or subject withdrawal of consent due to other comorbidities, etc. All these scenarios may constitute subject drop-outs. At the same time, it is assumed that follow-up compliance will be high in pacemaker population. The study attrition is assumed to be 10%.

6.2 Rationale and Considerations for Sample Size Determination

The study size is determined by the sample size required for the primary objective. Reynolds et al. reported that the Micra TPS and/or procedure related complication free survival probability through 6 months was 96%, (95% CI: 93.3%, 97.6%) in those who underwent Micra TPS implant procedures.³ Therefore, we conservatively assume that the expected performance (or, "Success Rate" in later text) in the study population will be 94%. The OPC is set as 83% (the same performance threshold in the FDA approved global study). The sample size calculation assumes the statistical analysis will be carried out on 0.05 significance level, 2-sided, 80% power and 10% study attrition. The minimum sample size requirement is 82. The sample size formula is displayed as following:

$$n = \frac{[Z_{1-\alpha/2} \sqrt{p_0(1-p_0)} + Z_{1-\beta} \sqrt{p_T(1-p_T)}]^2}{(p_T - p_0)^2};$$

Where p_T is the expected success rate, p_0 is the OPC value, Z value is under normal distribution, α is the type I error (or significance level, 0.05 is used) and β is the type II error (0.2 is used to ensure 80% power).

The sample size calculation employed a formula based on the binomial distribution of the asymptotic normality method because the success rate estimate given by the Kaplan-Meier method is consistent with the actual observed success rate if there are no drop-outs.

6.3 Sample Size Requirement for Each Study Center

The study will be conducted concurrently in multiple study sites. In principle, the number of enrollments at study sites will be evenly distributed to ensure adequate representativeness of each site. The actual number per center may fluctuate based on actual progress. The study will try to ensure the enrollment size at each center is relatively balanced, and for any center, the maximum enrollment number should not exceed 50% of the total study size.

6.4 Significant Level and Statistical Power

For this study, the statistical significance level is set at 0.05 (two-sided), and the statistical power is specified at 80%.

7. Statistical Methods

7.1 Study Subjects

7.1.1 Disposition of Subjects

Subject disposition will be summarized by a STROBE flow diagram, similar to the study flow diagram shown in **Figure 1**, but providing additional details on subject follow-up and attrition.

7.1.2 Clinical Investigation Plan (CIP) Deviations

A deviation is defined as an event within a study that did not occur according to the CIP or the Clinical Trial Agreement. Prior approval by Medtronic is expected in situations where the investigator anticipates, contemplates, or makes a conscious decision to deviate. Prior approval is not required when a deviation is necessary to protect the life or physical well-being of a subject in an emergency or in unforeseen situations beyond the investigator's control (e.g. subject failure to attend scheduled follow-up visits, inadvertent loss of data due to computer malfunction or inability to perform required procedures due to subject illness).

All study deviations must be reported on the CRF regardless of whether medically justifiable, pre-approved by Medtronic, an inadvertent occurrence, or taken to protect the subject in an emergency. The description of the deviation and justification must be documented.

Once a deviation has been identified it should be reported to Medtronic as soon as possible. Deviations may be identified through numerous sources, including but not limited to: telephone conversations, site monitoring, subject record, or data review.

It is the site's responsibility to report deviations in compliance with their Ethics Committee (EC)/Institutional Review Board (IRB) policies and/or local laws.

For medically justifiable conditions which preempt a subject's ability to complete a study-required procedure, it may be permitted to complete only one deviation which will apply to all visits going forward. This may also apply for other unforeseen situations (e.g. the subject permanently refuses to complete a study required procedure and the data will not contribute to the primary endpoint analysis). However, prior approval from Medtronic is required for such situations. (Example may include: unable to complete atrial threshold testing due to chronic atrial fibrillation (AF), etc.).

In the occurrence of a corrupted device interrogation file, Medtronic may request a deviation to document that a readable interrogation file is unavailable. Deviations for missing device interrogation file(s) and missing or incomplete electrical testing at the same visit may be reported on one deviation CRF.

In the event the deviation involves a failure to obtain a subject's informed consent or is made to protect the life or physical well-being of a subject in an emergency, the deviation must be reported to the IRB and Medtronic within five (5) working days. Reporting of all other study deviations should comply with IRB policies and/or local laws and must be reported to Medtronic as soon as possible upon the site becoming aware of the deviation. Reporting of deviations must comply with EC policies, local laws, and/or regulatory requirements.

Medtronic is responsible for analyzing deviations, assessing their significance, and identifying any additional corrective and/or preventive actions (e.g. amend the CIP, conduct additional training, and terminate the investigation). Repetitive or serious investigator compliance issues may represent a need to initiate a corrective action plan with the investigator and site, and in some cases, necessitate suspending enrollment until the problem is resolved or ultimately terminating the investigator's participation in the study.

Deviations from the CIP will be summarized in the clinical study report by coded category. The number of deviations per category, and the number and percentage of subjects with a deviation in each category will be reported.

7.1.3 Analysis Sets

The analysis sets for this study are defined as follows. Further detail regarding the analysis sets can be found in Section 7.1.4.

Full Analysis Set (FAS): This is a dataset defined as Intention-To-Treat principle, it refers to the set of all subjects who participates in the study and is exposed to the investigational device. In the event when primary endpoint data can't be collected from certain subjects, censoring or additional analysis may be applied.

Per Protocol Set (PPS): A subset of study subjects who complies to study protocol (The subject who has a violation related to study inclusion/exclusion criterion will be excluded from the PPS).

Safety Analysis Set (SS): The same definition as FAS should be used. Therefore, no additional definition is provided here.

The primary objective analysis will be performed on the FAS and PPS. The electrical parameters (secondary objective #1) will be analyzed on the FAS and PPS. The safety assessment (secondary objective #2), and all baseline demographic summary will be performed on the FAS. [REDACTED]

[REDACTED] The baseline demographic summary, secondary objectives, [REDACTED] will be performed with available data from the database.

7.1.4 Pre-specified Protocol Deviations and Flow Chart of Analysis Population Set Determination

The following pre-specified protocol deviation items will be checked according to the principle of statistical analysis by SAS programming. These items may be a little bit different from the protocol deviations reported by clinical operation which are collected by CRF.

(1) Withdrawal of informed consent: Subjects obtain registration number, but do not end up using the study device. These are subjects who have had no exposure to the study device (i.e., no Successful or Unsuccessful Implant form is completed).

(2) Violation of inclusion and exclusion criteria: Subjects do not meet the inclusion criteria set in the protocol or meet the exclusion criteria set in the protocol, and this protocol deviation may severely affect the results of primary endpoint. Whether protocol deviation severely affect the results of primary effective endpoints shall be judged together by sponsor, investigators and statistician through discussion at a final data review meeting prior to final database lock.

(3) Lost to follow-up : Subjects are unable to obtain the primary endpoint (i.e. the primary endpoint is identified as true missing). If a subject has a primary endpoint failure, and later is lost to follow-up (prior to 183 days), the subject will still be included in the primary endpoint analysis. This criterion will only be used for the primary endpoint.

(4) Out of time window: The difference between the 6-month follow-up date after operation and operation date of subjects is less than 183 days and this may severely affect the results of primary endpoint. Whether protocol deviation severely affects the results of primary endpoint will be judged together by sponsor, investigators and statistician by discussion at the final data review meeting prior to final database lock. If a subject has a primary endpoint failure, and later has the 6 month visit too early (prior to 183 days), the subject will still be included in the primary endpoint analysis.

(5) Application of Non-study devices: The device implanted for subject is not the study device specified in study protocol or the subject ended up receiving no device at all. If a subject has a primary endpoint failure during the unsuccessful implant attempt, the subject will still be included in the primary endpoint analysis.

[figure not shown]
FAS= Number of the enrolled patients – Number of patients who withdraw informed consent;
PPS=FAS – Number of patients who severely violate study protocol;

Number of patients who severely violate study protocol = Number of patients who violate inclusion and exclusion criteria + Lost to follow-up + Number of patients with out of time window + Number of patients with application of Non-study devices

Priority level of severely violating study protocol: Lost to follow-up, application of non-study devices, violation of inclusion and exclusion criteria, out of time window. If subjects meet two or more above severe cases of protocol deviation, they will be classified in accordance with above priority level of protocol deviation.

The serious protocol deviations of subjects will be listed based on actual cases after final data review meeting determination. (For example, if the number of subjects who are out of time window is 0, this item will not be displayed in the table). Additionally, the subjects who were withdrawal of informed consent or serious protocol deviations will be listed, including the center number, registration number, gender, age, deviation type, deviation reason, FAS and PPS.

Figure 2: Flow Chart of Analysis Population Set Determination

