14.1.8. Deviation from Pre-specified Analysis Plan

The statistical analysis plan will be finalized by the sponsor and the primary investigator before the data is locked for analysis. The analysis plan may be modified to consider actual scenarios observed during the study phase before its being final approved. In principle, no major analysis methods or definition of analysis sets should be changed. All versions will be recorded.

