14.1.9. Criteria and Rationale for Selection of Subjects for Analysis

Statistical analysis sets should be clearly defined prior to the time when analysis is carried out. The analysis sets for this study are defined as follows:

Confidential

Full Analysis Set (FAS): This is a dataset defined per Intention-To-Treat principle, it refers to the set of all subjects who participates in the study and is exposed to the investigational device. In the event when data can't be collected from certain subjects, censoring or additional analysis may be applied..

Per Protocol Set (PPS): A subset of study subjects who complies to study protocol (The subject who has a violation related to study inclusion/exclusion criterion will be excluded from the PPS).

Safety Analysis Set (SS): The same definition as FAS should be used. Therefore, no additional definition is provided here.

The primary objective analysis will be performed on the FAS; all baseline demographic data and secondary objectives will be based on the FAS or PPS, and the safety assessment will be performed on the FAS. The electrical parameters will be analyzed on PPS.

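### SAP 7.1.4(2) makes exclusion of eligibility violators from the per-protocol set a judgement about the primary result, where protocol 14.1.9 and SAP 7.1.3 exclude them all

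*SAP*

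**What the plan says.** Protocol 14.1.9 defines the PPS without a severity test: "The subject who has a violation related to study inclusion/exclusion criterion will be excluded from the PPS". SAP 7.1.3 repeats that sentence and refers to 7.1.4 for further detail.

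SAP 7.1.4(2) then counts an eligibility violation only if a second condition is met: "and this protocol deviation may severely affect the results of primary endpoint. Whether protocol deviation severely affect the results of primary effective endpoints", and it continues that this "shall be judged together by sponsor, investigators and statistician through discussion at a final data review meeting prior to final database lock".

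Later in SAP 7.1.4 the PPS is set equal to the FAS minus severe violators, but the eligibility term in that sum carries no severity wording: "Number of patients who severely violate study protocol = Number of patients who violate inclusion and exclusion criteria".

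Three other statements bear on the point:
- Protocol 14.1.8, on finalising the SAP: "In principle, no major analysis methods or definition of analysis sets should be changed".
- SAP 7.1.3, on use of the sets: "The primary objective analysis will be performed on the FAS and PPS". Protocol 14.1.9 and SAP 7.9.1.3 name only the FAS for the primary objective.
- The electrical parameters are analysed on the PPS in protocol 14.1.9, and on the FAS and PPS in SAP 7.1.3.

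**The concern.** A violator judged not severe is out of the PPS under protocol 14.1.9 and SAP 7.1.3, but in it under SAP 7.1.4(2). Two programmers working from different sections would build different sets.

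The added test is also of the wrong kind. It asks about the effect on the primary endpoint results, which is hard to answer without regard to whether the subject had the endpoint. The design is a "prospective, multi-center, single arm human clinical trial utilizing OPC", so there is no treatment assignment to mask. Under protocol 13.1 investigators supply the event classification and receive the committee's rationale when it disagrees. SAP 7.8 allows descriptive summaries during the study. Neither document masks the data review meeting. That outcomes will be known there is an inference, since the SAP fixes only the timing, before final lock. It is a reasonable one.

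At stake is the value of the PPS result as support for the FAS result. It shows robustness only if membership cannot depend on outcome.

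**Working it through.** **The plan's own figure.** SAP 6.2 gives p0 = 0.83, pT = 0.94, two-sided alpha 0.05, power 80% and attrition 10%.

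n = [1.960 × √(0.83 × 0.17) + 0.842 × √(0.94 × 0.06)]² / 0.11² = (0.7362 + 0.1999)² / 0.0121 = 72.42, rounded up to 73. Then 73 / 0.9 = 81.1, rounded up to 82. The stated 82 reproduces and is not in dispute.

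**Method for the illustration.** SAP 7.9.1.2 specifies Kaplan-Meier with log-log 95% limits and success if the lower limit exceeds 83%. With no censoring and x failures in n:

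- S = 1 − x/n
- se = √(S(1 − S)/n), which is Greenwood's formula without censoring
- s = se / |S × ln S|
- lower limit = S^exp(1.96 × s)

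Worked once for 7/82: S = 0.9146, se = 0.0309, ln S = −0.0892, s = 0.378, exp(1.96 × 0.378) = 2.098, lower limit = 0.9146^2.098 = 0.829.

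**Assumptions, not in the documents.** FAS of 82 with 7 failures; two eligibility violators, one with a primary failure and one event-free; no other PPS exclusions.

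| Rule | Violators removed | PPS failures/n | Lower limit | Above 83%? |
|---|---|---|---|---|
| Protocol 14.1.9, SAP 7.1.3 | both | 6/80 | 84.1% | yes |
| SAP 7.1.4(2) | both | 6/80 | 84.1% | yes |
| SAP 7.1.4(2) | failed one only | 6/81 | 84.3% | yes |
| SAP 7.1.4(2) | event-free one only | 7/81 | 82.7% | no |
| SAP 7.1.4(2) | neither | 7/82 | 82.9% | no |

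The unconditional rule gives one answer, fixed by eligibility facts. The discretionary rule gives four possible sets, two on each side of 83%. The FAS result is 7/82, 82.9%, in every row.

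**The case against.** **The FAS decides the objective.** Protocol 14.1.9 and SAP 7.9.1.3 place the primary objective on the FAS. SAP 7.1.3 adds the PPS, but nothing says that a PPS pass can rescue a FAS failure. This stands and limits the impact.

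**SAP 7.1.4 is offered as further detail.** It could be read as putting the short definition into operation, and it requires a listing of serious deviations with reasons and set membership. In part this stands: removals will be visible. But the section narrows an unconditional exclusion, which protocol 14.1.8 discourages, and a violator judged not severe may not appear in that listing.

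**Stronger readings that the documents do not support.**
- *The discretion favours the device, and one removed subject turns a fail into a pass.* Going from 7/82 (82.9%) to 6/81 (84.3%) compares the FAS with a PPS, not one PPS rule with the other. The protocol rule removes the same failed violator and gives 84.1%, also a pass; the rules then differ by about 0.2 points. With 6 failures left, the limit drops below 83% only at n = 74 (82.8%; n = 75 gives 83.06%). For selective retention to change that pass, seven event-free violators would have to be kept besides the failed one removed. The discretion can equally keep a failed violator, which works against the device.
- *Item (2) is defective because, unlike items (3) to (5), it has no clause retaining subjects with a primary failure.* The unconditional rule has no such clause either, so its absence does not separate the two rules.
- *The meeting will see outcomes.* No passage says so. What can be said is that none prevents it.

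**Conclusion.** The contradiction is on the page, and the point holds in this limited form: the SAP has two eligibility rules for the PPS, and one of them rests on an unmasked judgement that refers to the primary endpoint. Near the boundary that judgement, not eligibility alone, can decide whether the PPS limit clears 83%. In the illustration the limit ranges from 82.7% to 84.3%, against a single 84.1% under the protocol rule. This assumes 7 failures in 82, no censoring and two violators. The documents give no violator count, and enrolment itself requires that all criteria be met, so the number may be small or zero.

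The effect is confined to the PPS analyses: the supportive analysis of the primary objective added in SAP 7.1.3, and the electrical parameters. The FAS and the sample size are untouched. It should be corrected before the data review meeting, but it does not threaten the deciding analysis.

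**What to change.** In SAP 7.1.4(2), delete the condition about severely affecting the primary endpoint and the sentence giving that judgement to the meeting. State instead that any subject whose baseline data show an inclusion criterion not met or an exclusion criterion met is removed from the PPS, determined from baseline data only and without reference to endpoint status. This restores the rule in protocol 14.1.9 and SAP 7.1.3 and agrees with the unqualified eligibility term in the PPS sum.

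Item (4), on 6-month visits made too early, uses the same test judged by the same group. Replace it with a rule based on visit dates alone, keeping its existing clause for subjects who already had a primary endpoint failure.

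The cost is SAP wording only. The downside is that subjects with trivial eligibility deviations also leave the PPS, as the protocol already requires.
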